2.2 Secondary Goals

1. To identify biomarkers that predict response rates of untreated smoldering MM and MM patients to a combination of an immunomodulator and dexamethasone.
2. To compare response rates of MM among AA and white patients to a combination of an immunomodulator and dexamethasone.
3. To establish correlation of biomarkers in treated MM patients with the combination of an immunomodulator and dexamethasone to the depth of hematological response observed in new or previously treated patients.

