5.0 Grouping Factor

5.1 Multiple Myeloma Cohort: Cohort A (Smoldering MM), Cohort B (Newly Diagnosed MM), Cohort C (Relapsed/Refractory MM) and Cohort D (Relapsed on Len maintenance).

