16.0 Statistical Considerations and Methodology

16.1 Overview:

This is a pilot study to determine the response rates (>PR) of the combination of an immunomodulator and dexamethasone in Multiple Myeloma (MM) patients of each clinically relevant biomarker. This combination will be evaluated in four cohorts: Cohort A (Smoldering MM), Cohort B (Newly Diagnosed MM), Cohort C (Relapsed/Refractory MM) and Cohort D (Relapsed on Len maintenance). This study will not utilize a formal statistical design but will focus more on estimation rather than hypothesis testing.

16.11 Primary Endpoint: The primary endpoint of this trial is to estimate (>PR) response rates (RR) after one cycle of treatment. Biomarkers of interest will be identified and categorized into clinically relevant groups (e.g. positive vs. negative) by evaluating baseline and post treatment (after cycle one) biospecimens. RR will be estimated within each biomarker.

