16.2 Statistical Design

Due to the lack of data to identify relevant biomarkers, the estimation of RR would be of interest. In each group, the response rates will be examined to see if there's any preliminary evidence to suggest further studies. This study will not utilize a formal statistical design.

For each biomarker category, the RR will be estimated by the number of patients who achieve a PR or better divided by the total number of evaluable patients in each cohort. Exact binomial 95% confidence intervals for these rates will be calculated.

16.22 Sample Size: A maximum of 30 evaluable patients will be accrued in cohort A and B and 60 patients in cohort C and D respectively. We anticipate accruing an additional 2 in cohort A and B and 3 in cohort C and D to account for ineligibility, cancellation, major treatment violation, or other reasons. Therefore, the maximum projected accrual is 190 patients (A: 32, B: 32, C: 63 and D: 63).

16.23 Accrual Rate and Study Duration: The anticipated accrual rate is 6 evaluable patients per month. Therefore, the accrual period for this pilot study is expected to be approximately 32 months. The final analysis can begin approximately 35 months after the trial begins, i.e. as soon as the last patient has been observed for 1 months and allowing 2 months for data entry.

16.24 Other considerations: Adverse events, quality/duration of response, and patterns of treatment failure observed in this study, as well as scientific discoveries or changes in standard care will be taken into account in any decision to terminate the study

16.3 Analysis Plan.

The analysis for this study is planned to start after data maturity has occurred. It is anticipated that the earliest date in which the result will be available via manuscript, abstract or presentation after the last registered patient has been followed for at least 1 month.

16.31 Primary Outcome Analyses:

Each cohort (A-D) will be evaluated separately and independently.

16.311 Definition:

The primary endpoint of this study is RR after 1 cycle of treatment. RR is defined as a binary variable. A success will be defined as patient who achieve a response of a PR or better using the IMWG criteria (Section 11.0) after one cycle of treatment. All patients meeting eligibility criteria who have signed a consent form, who complete at least one cycle of treatment and have successfully submitted biospecimens (pre and post treatment) will be evaluable for the endpoint.

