Estimation: For each biomarker of interest, RR will be calculated by the number of successes divided by the total number of evaluable patients in each cohort.

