16.32 Secondary Outcome Analyses

16.321 Biomarkers and RR will be analyzed using logistic regressions to identify predictive biomarkers.

16.322 RR among African American (AA) patients and white MM patients will be evaluated after one cycle of treatment. Chi-Square (or Fischer Exact) test and 95% confidence intervals will be estimated to compared AA and white patients descriptively.

16.323 Correlation between the depth of hematological responses and biomarkers will be estimated. Logistic regressions and chi square (or Fischer exact) testing will be utilized.

16.33 Data & Safety Monitoring:

The principal investigator(s) and the study statistician will review the study at least twice a year to identify accrual, adverse event, and any endpoint problems that might be developing. The Mayo Clinic Cancer Center (MCCC) Data Safety Monitoring Board (DSMB) is responsible for reviewing accrual and safety data for this trial at least twice a year, based on reports provided by the MCCC Statistical Office.

Adverse Event Stopping Rules: (Each cohort will be analyzed separately) The stopping rules specified below are based on the knowledge available at study development. We note that the Adverse Event Stopping Rule may be adjusted in the event of either (1) the study re-opening to accrual or (2) at any time during the conduct of the trial and in consideration of newly acquired information regarding the adverse event profile of the treatment(s) under investigation. The study team may choose to suspend accrual because of unexpected adverse event profiles that have not crossed the specified rule below.

Accrual will be temporarily suspended to this study if at any time we observe events considered at least possibly related to study treatment (i.e. an adverse

event with attribute specified as “possible”, “probable”, or “definite”) that satisfy either of the following:

- If 3 or more out of the first 10 treated patients experience grade 4+ non-hematological toxicities
- If after the first 10 patients have been treated, 30% of patients experience grade 4+ non-hematologic toxicities

We note that we will review grade 5 adverse events deemed “unrelated” or “unlikely to be related”, to verify their attribution and to monitor the emergence of a previously unrecognized treatment-related adverse event.

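### Section 16.322 compares AA and white response with an unstratified test and does not say whether Cohorts A–D are pooled or whether smoldering Cohort A is included

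*Combined protocol and SAP*

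**What the plan says.** Secondary goal 2 (section 2.2) is "To compare response rates of MM among AA and white patients to a combination of an immunomodulator and dexamethasone". Its analysis, in 16.322, is response after one cycle in the two groups: "Chi-Square (or Fischer Exact) test and 95% confidence intervals will be estimated to compared AA and white patients descriptively". Neither place mentions cohort, pooling, stratification or a covariate.

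Elsewhere the plan works by cohort. Section 16.31, headed as the primary outcome analyses, says "Each cohort (A-D) will be evaluated separately and independently", and the estimation paragraph of 16.311 says "RR will be calculated by the number of successes divided by the total number of evaluable patients in each cohort". The adverse event stopping rule in 16.33 repeats that cohorts are analysed separately. Section 16.32 has no such statement.

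Cohort sizes are in 16.22: "A maximum of 30 evaluable patients will be accrued in cohort A and B and 60 patients in cohort C and D respectively". Section 16.43 sets the AA target for the whole trial (15%, shown as 29 of 190), with no target per cohort.

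On Cohort A the documents point both ways. Section 5.1 defines the grouping factor as "Multiple Myeloma Cohort: Cohort A (Smoldering MM), Cohort B (Newly Diagnosed MM), Cohort C (Relapsed/Refractory MM) and Cohort D (Relapsed on Len maintenance", and 16.1 likewise lists smoldering disease among the cohorts of MM patients. The rationale in 1.2 and secondary goal 1, however, name smoldering MM and MM as two populations, and goal 2 and 16.322 mention only MM.

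**The concern.** The four cohorts are different disease settings, and cycle 1 treatment options differ between A/B and C/D (section 7.1). Section 1.1 also reports different overall response rates by setting. If AA patients are spread over the cohorts differently from white patients, a crude pooled difference mixes race with disease setting and can move in either direction. At stake is the interpretability of the estimate for secondary goal 2. Cohort is already recorded for every patient as the grouping factor, so the plan can avoid this with information it holds.

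**Working it through.** **1. The plan's own figures.** Accrual: 32 + 32 + 63 + 63 = 190. AA target: 0.15 × 190 = 28.5, shown as 29, and 29 + 161 = 190. These reproduce. Evaluable patients: 30 + 30 + 60 + 60 = 180, of whom 15% is 27. Spread in proportion, that is 4.5 / 4.5 / 9 / 9 in A/B/C/D.

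**2. What separate analyses would give.** The 95% half-width of a difference is 1.96 × √[p(1−p)(1/n_AA + 1/n_W)], with p between 0.3 and 0.5:
- A or B (4 v 26, or 5 v 25): 44–53 points
- C or D (9 v 51): 32–35 points
- pooled (27 v 153): 19–20 points

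This makes pooling a plausible intention. It does not show that pooling is intended.

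**3. Shift from cohort mix.** With no race effect inside any cohort, the expected crude difference is Σ(a_k p_k)/27 − Σ(w_k p_k)/153. Here a_k and w_k are the AA and white counts in cohort k, p_k is the response rate in that cohort, and every non-AA patient is counted as white. It is zero if all p_k are equal, or if the AA share is the same in each cohort.

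No one-cycle rate is given for any cohort, and no rate of any kind for smoldering disease. Overall rates from section 1.1 stand in, with A set equal to B and Cohort A included:
- newly diagnosed: 68–91%
- previously treated, lenalidomide: 48–61% and 46–57%
- pomalidomide: 40% or 47% in lenalidomide-refractory patients; 35–42% with the 4 mg schedule

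**4. Chance imbalance.** The 27 AA patients were drawn at random from 30/30/60/60 (200,000 multivariate hypergeometric draws).

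| Rates A/B/C/D (%) | Mean absolute shift (points) | 95th percentile |
|---|---|---|
| 68/68/61/47 | 1.5 | 3.7 |
| 68/68/48/40 | 2.0 | 4.9 |
| 91/91/46/35 | 4.0 | 9.8 |
| equal in all cohorts | 0 | 0 |

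The signed mean is zero in every row. If one-cycle rates were half those in the first two rows (an assumption), the mean absolute shift would be 0.7–1.0.

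The sampling SD at a 4/5/9/9 split with rates 68/68/48/40 uses Σp(1−p) = 0.2176 + 0.2496 + 0.24 = 0.7072, because A and B together hold 9 AA and 51 white patients. SD = √(9 × 0.7072/27² + 51 × 0.7072/153²) = √(0.00873 + 0.00154) = 10.1 points.

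**5. Systematic imbalance.** Fixed splits at rates 68/68/48/40:
- 7/7/7/6 (14 in A/B): AA 1528/27 = 56.6%, white 7832/153 = 51.2%, shift +5.4
- 10/9/4/4 (19 in A/B): AA 1644/27 = 60.9%, white 7716/153 = 50.4%, shift +10.5
- 3/3/11/10 (6 in A/B): shift −3.0
- 5/6/2/14: AA 1404/27 = 52.0%, white 7956/153 = 52.0%, shift 0

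At these rates a shift of 5–10 points needs about 14–19 AA patients in A/B, where 9 are expected. The threshold depends on the rates. At 68/68/61/47 the same two splits give +3.4 and +6.1. At 91/91/46/35 a milder split, 6/6/8/7, already gives 1705/27 − 8615/153 = 63.1 − 56.3 = +6.8.

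**6. Stratified estimate.** The Mantel-Haenszel risk difference weights each cohort by a_k w_k/n_k. In 100,000 simulated trials per setting at the first two rate sets, its mean was zero to within 0.1 point. Its SD was 10.1 against 10.1 crude at 4/5/9/9, and 10.5–10.6 against 9.9–10.0 crude at 10/9/4/4. With race-independent mixing it was 10.2, against 10.3–10.5 crude.

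**The case against.** The strongest reply is that wherever section 16 states the scope of a response or safety analysis, the unit is the cohort. On that reading 16.322 inherits the rule and there is no pooled estimate to confound. Small cells do not rule this out: the plan already splits 30-patient cohorts by biomarker, disclaims a formal design, adds no sample size for subsets, and offers Fisher's test. This is a fair reading, but it is not written for 16.32, and the plan does restate the rule for the stopping boundary. The text leaves both readings open, and a sentence in 16.322 is needed under either.

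It is also true that the comparison is labelled descriptive in a pilot that "will focus more on estimation rather than hypothesis testing".

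A reader might infer more than the documents support:
- **That the plan pools the cohorts.** It does not say so. The trial-wide AA target only makes pooling plausible.
- **That the crude difference is biased whenever race mix and response both vary by cohort.** The 5/6/2/14 split is a counterexample: both vary and the shift is exactly zero. Confounding can occur under those conditions but need not.
- **That Cohort A is in the comparison.** Sections 5.1 and 16.1 suggest yes; section 1.2 and goal 1 suggest no. It is open.
- **That the 1.5–4 points measure systematic confounding.** They come from draws in which race is unrelated to cohort, so they describe chance imbalance only. Section 1.2 mentions lesser AA access to IMiDs, which could affect who qualifies for Cohort D, but no AA share by cohort is given.

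**Conclusion.** The point holds as a conditional one, and it is minor. Section 16.322 names a crude test, leaves pooling and Cohort A unstated, and would allow a pooled difference that partly reflects cohort mix.

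The size is illustrative. With 27 AA of 180, Cohort A included and no race effect, chance imbalance shifts the estimate by about 1.5–4 points on average (95th percentile about 4–10), in either direction, against a sampling SD of about 10. A systematic shift of 5–10 points would need a marked concentration of AA patients in A/B, about 14–19 at rates 68/68/48/40, and no section documents one. All of this rests on overall response rates standing in for unknown one-cycle rates. If one-cycle rates are equal across cohorts, or the cohorts are never pooled, the problem vanishes. No trial decision depends on the comparison.

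**What to change.** In 16.322:
1. State which cohorts enter the AA–white comparison, settling Cohort A either way, and whether they are pooled.
2. Tabulate response by race within each cohort, with exact 95% confidence intervals.
3. For any pooled comparison, report a Mantel-Haenszel risk difference stratified by cohort with its 95% confidence interval, as description. If a p-value is shown, use the Cochran-Mantel-Haenszel test (exact if sparse) in place of the crude test.

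The cost is SAP wording only, best settled before response data are seen. Precision loss is negligible: none at a proportional mix and about half a point of SD at the most unequal split examined. The within-cohort table will be very imprecise in A and B (3 responders of 5 has an exact 95% interval of 15–95%), so it can only describe.

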7.0 Protocol Treatment

7.1 Treatment Schedule

Cohort A and B Cycle 1

Treatment medication table. Patient may receive Lenalidomide OR Lenalidomide + Dexamethasone.

Agent	Dose Level	Route	Day	Re Rx
Lenalidomide	25 mg*	Oral	Cycle 1: Day 1-14	Cycle 1: 21 days
Dexamethasone	40 mg**	Oral	Cycle 1: Day 1 ,8, ,15	Cycle 1: 21 days

Cycle 1 length = 21 days

* Starting dose will be determined as per the creatine clearance below (see 7.12)

**The dose of dexamethasone used can be determined by the treating physician and omitted if needed.

Cohort C and D Cycle 1

Treatment medication table. Patient may receive Lenalidomide + Dexamethasone OR Pomalidomide + Dexamethasone.

Agent	Dose Level	Route	Day	ReRx
Lenalidomide	25 mg*	Oral	Cycle 1: Day 1-14	Cycle 1: 21 days
Pomalidomide	4 mg	Oral	Cycle 1: Day 1-21	Cycle 1: 21 days
Dexamethasone	40 mg**	Oral	Cycle 1: Day 1 ,8, ,15	Cycle 1: 21 days

Cycle 1 length = 21 days

* Starting dose will be determined as per the creatinine clearance below (see 7.12)

** The dose of dexamethasone used can be determined by the treating physician and omitted if needed.

Cohort A and B Cycles 2-6

Treatment Medication Table. Patient may receive Lenalidomide based regimens.

Agent	Dose Level	Route	Day	Re Rx
Lenalidomide	25 mg*	Oral	Cycle 2-6: Day 1-21	Cycles 2-6: 28 days
Dexamethasone	40 mg**	Oral	Cycle 2-6: Day 1 ,8, ,15, 22	Cycles 2-6: 28 days

Note: Standard of care agents can be added for cycles 2-6 as long as the regimen contains lenalidomide

Cycles 2-6 length = 28 days

* Any dose-adjustments will be determined as per the creatine clearance below (see 7.12).

** The dose of dexamethasone used can be determined by the treating physician and omitted if needed.

Cohort C and D Cycles 2-6

Treatment medication table. Patient may receive Lenalidomide based regimen OR Pomalidomide based regimen.

Agent	Dose Level	Route	Day	ReRx
Lenalidomide	25 mg*	Oral	Cycles 2-6: Day 1-21	Cycles 2-6: 28 days
Pomalidomide	4 mg	Oral	Cycles 2-6: Day 1-21	Cycles 2-6: 28 days
Dexamethasone	40 mg**	Oral	Cycle 2-6: Day 1,8,15,22	Cycles 2-6: 28 days

Note: Standard of care agents can be added for cycles 2-6 as long as the regimen contains lenalidomide or pomalidomide

Cycles 2-6 length = 28 days

* Any dose-adjustments will be determined as per the creatinine clearance below (see 7.12).

** The dose of dexamethasone used can be determined by the treating physician and omitted if needed.

7.12

Creatinine Clearance (CrCl)	Lenalidomide Dose

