10.0 Adverse Event (AE) Monitoring and Reporting

The site principal investigator is responsible for reporting any/all serious adverse events to the sponsor as described within the protocol, regardless of attribution to study agent or treatment procedure.

The sponsor/sponsor-investigator is responsible for notifying FDA and all participating investigators in a written safety report of any of the following:

- Any suspected adverse reaction that is both serious and unexpected.
- Any findings from laboratory animal or *in vitro* testing that suggest a significant risk for human subjects, including reports of mutagenicity, teratogenicity, or carcinogenicity.
- Any findings from epidemiological studies, pooled analysis of multiple studies, or clinical studies, whether or not conducted under an IND and whether or not conducted by the sponsor, that suggest a significant risk in humans exposed to the drug

- Any clinically important increase in the rate of a serious suspected adverse reaction over the rate stated in the protocol or Investigator's Brochure (IB).

Summary of SAE Reporting for this study
(please read entire section for specific instructions):

WHO:	WHAT form:	WHERE to send:
Mayo Clinic Sites	Pregnancy Reporting http://ctep.cancer.gov/protocolDevelopment/electronic_applications/docs/PregnancyReportFormUpdated.pdf	Mayo Sites – attach to MCCC Electronic SAE Reporting Form http://livecycle2.mayo.edu/workspace/?startEndpoint=MC4158-56/Processes/MC4158-56-Process.MC4158-56 Will automatically be sent to [contact] and [contact]
Mayo Clinic Sites	Mayo Clinic Cancer Center SAE Reporting Form: http://livecycle2.mayo.edu/workspace/?startEndpoint=MC4158-56/Processes/MC4158-56-Process.MC4158-56	Will automatically be sent to [contact] and [contact]
Mayo Clinic Sites	Mayo Clinic Cancer Center SAE Reporting Form: http://livecycle2.mayo.edu/workspace/?startEndpoint=MC4158-56/Processes/MC4158-56-Process.MC4158-56 AND attach MedWatch 3500A: http://www.fda.gov/downloads/AboutFDA/ReportsManualsForms/Forms/UCM048334.pdf	Will automatically be sent to [contact] and [contact]

Definitions

Adverse Event

Any untoward medical occurrence associated with the use of a drug in humans, whether or not considered drug related.

Suspected Adverse Reaction

Any adverse event for which there is a reasonable possibility that the drug caused the adverse event.

Expedited Reporting

Events reported to sponsor within 24 hours, 5 days or 10 days of study team becoming aware of the event.

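### Consider adding a pooled pomalidomide count to the 16.33 toxicity pause: it is counted only by disease cohort, so it can miss a clearly more toxic pomalidomide that is the minority drug in both Cohorts C and D

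*Combined protocol and SAP*

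**What the plan says.** Section 16.33 opens its rule with "Adverse Event Stopping Rules: (Each cohort will be analyzed separately". The consequence of a crossing is stated as "Accrual will be temporarily suspended to this study if at any time we observe events considered at least possibly related to study treatment". There are two triggers, both for grade 4+ non-hematologic events: 3 or more of the first 10 treated patients, and then "If after the first 10 patients have been treated, 30% of patients experience grade 4+ non-hematologic toxicities".

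Section 7.1 sets the drugs. For cycle 1 of Cohorts A and B: "Patient may receive Lenalidomide OR Lenalidomide + Dexamethasone". For cycle 1 of Cohorts C and D: "Patient may receive Lenalidomide + Dexamethasone OR Pomalidomide + Dexamethasone". For later cycles in C and D: "Standard of care agents can be added for cycles 2-6 as long as the regimen contains lenalidomide or pomalidomide". No section says who gets which drug, and section 5.1 names cohort as the only grouping factor. Section 16.22 plans 32 patients each in A and B and 63 each in C and D.

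Below the boundary, 16.33 leaves room for judgement: "The study team may choose to suspend accrual because of unexpected adverse event profiles that have not crossed the specified rule below". It also allows the rule to be adjusted at any time, and has the study team and the DSMB each review at least twice a year.

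**The concern.** Cohorts A and B contain one IMiD, so their cohort count is also a lenalidomide count. As 16.33 is worded, a crossing there suspends the whole study. Pomalidomide has no such cohort. Its events are divided by a denominator that includes lenalidomide patients, and are split over two cohorts that are never combined.

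The documents also give a reason to look at pomalidomide separately, although not evidence of excess toxicity. In cycle 1 it is given on all 21 days of a 21-day cycle, while lenalidomide stops at day 14 (7.1).

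At stake is whether a high pomalidomide toxicity rate stops accrual by rule, or only if someone decides to act.

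**Working it through.** **The plan's own figures.** 32 + 32 + 63 + 63 = 190, as in 16.22. 3/10 = 30%, so the two triggers agree. 16.33 states no operating characteristics for the rule.

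**Inputs.** From the documents: the triggers (16.33), cohort sizes (16.22), drugs by cohort (7.1) and 6 patients a month (16.23). Assumed: the pomalidomide share *s* and the grade 4+ non-hematologic rates for pomalidomide (pP) and lenalidomide (pL).

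**A count by hand.** With 63 patients the trigger at full accrual is 19 events (0.30 × 63 = 18.9). At a 30% share, about 19 patients receive pomalidomide and 44 lenalidomide. Suppose 8/19 (42%) and 2/44 (5%) have an event. The cohort shows 10/63 = 16%, far below the trigger.

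**Chance of crossing.** The cohort event rate is s × pP + (1 − s) × pL. An exact patient-by-patient binomial recursion gives P, the chance of 3 or more events by patient 10, or of events/n ≥ 0.30 at any n ≥ 10. For C or D the chance is 1 − (1 − P_C)(1 − P_D). The pooled count applies the same recursion to the pomalidomide patients, 63 × (s_C + s_D) in number.

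For pP = 40%, pL = 5%:

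| Share C / D | Cohort rates | P_C, P_D | C or D pauses | Pooled pomalidomide count |
|---|---|---|---|---|
| 20% / 20% | 12%, 12% | 0.128, 0.128 | 24% | 95% (n = 25) |
| 30% / 30% | 15.5%, 15.5% | 0.241, 0.241 | 42% | 97% (n = 38) |
| 10% / 50% | 8.5%, 22.5% | 0.052, 0.550 | 57% | 97% (n = 38) |
| 20% / 80% | 12%, 33% | 0.128, 0.928 | 94% | 99% (n = 63) |

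First row: 0.2 × 0.40 + 0.8 × 0.05 = 0.12, and 1 − 0.872² = 0.24.

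For pP = 30%, pL = 10%, where pomalidomide sits at the trigger level: at shares of 20% and 30% in both cohorts, C or D pauses with probability 34% and 45%, against 76% and 81% pooled. A or B also pauses by chance with probability 0.154. Crediting that gives 1 − 0.659 × 0.846 = 44% and 1 − 0.548 × 0.846 = 54%.

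**Why only pomalidomide.** With 32 patients each, A or B pauses with probability 95.8% at a true lenalidomide rate of 30% and 99.9% at 40%, if its toxicity there resembles that in C and D.

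**Exposure.** Treatment lasts 21 + 5 × 28 = 161 days. In simulations with event times spread over those days, at 40% v 5% and shares of 20% to 50%, the mean number of pomalidomide patients treated before a pause or full accrual falls from roughly 21-30 to roughly 10-15 with the added count.

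All of these calculations keep each patient on the drug started in cycle 1.

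**The case against.** The strongest reply is that the contrast is assumed. Nothing in the documents says pomalidomide causes several times as many grade 4+ non-hematologic events as lenalidomide, and the toxicity lists in 15.17 and 15.27 overlap widely. That stands: the size of the gap is conditional on it.

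Second, Cohort D has relapsed with lenalidomide maintenance as its most recent therapy (3.12), so pomalidomide may well predominate there. That also stands. A reader might infer that the gap is large at any overall share of half or less. It is not: at 20% in C and 80% in D, which is half overall, the figures are 94% and 99%.

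Third, other safeguards exist. Serious grade 4-5 events are reported within 24 hours (10.41). Section 8.41 reduces or stops pomalidomide in the affected patient. Section 10.0 requires notification of "Any clinically important increase in the rate of a serious suspected adverse reaction over the rate stated in the protocol", and 10.32 places a similar duty on sites. Section 16.24 brings adverse events into any decision to terminate, and 16.33 adds discretionary suspension and DSMB review. A 40% rate would probably be noticed. But none of these sets a drug-level threshold or pauses accrual by itself. The rate-increase duties have no numeric trigger, and the toxicity lists give frequency bands rather than grades.

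Fourth, a drug count is imperfect. Agents may be added in cycles 2-6, and nothing bars a switch between the two IMiDs. This limits what a crossing means and shapes the wording of the fix.

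**Conclusion.** The point holds as a low-cost improvement to consider, not as an error. If pomalidomide is the minority drug in both C and D and clearly more toxic than lenalidomide, the mandatory pause is likely to miss it. In the 40% v 5% cases with a minority share in both cohorts, C or D pauses 24% to 42% of the time, against 95% to 97% with a pooled count. The smaller contrast leaves a smaller but real gap.

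Three stronger readings are tempting and not supported:

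- **That the plan breaches its own 30% limit for a drug.** The 30% is a cohort trigger; no drug limit exists.
- **That lenalidomide needs its own count too.** Cohorts A and B already track it, unless its toxicity differs by disease setting.
- **That the added count would stop pomalidomide after 8 or 9 patients.** That needs every event to be known before the next patient enrols; roughly 10-15 is more realistic.

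Confidence is medium, because the shares and rates are all assumed.

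**What to change.** Keep the cohort rule. Add to 16.33 that the same two triggers (3 or more of the first 10 treated; 30% thereafter) also apply to pomalidomide-treated patients pooled across Cohorts C and D. Patients enter this count when they first receive pomalidomide, and only events during pomalidomide or within 30 days of it count. This deals with switching. A crossing suspends new pomalidomide starts pending study team and DSMB review. It prompts review and does not prove that pomalidomide is the cause.

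Also tabulate adverse events by IMiD in the DSMB reports. The table matters because the count takes time. At a 20% share and a 40% rate, even with events known at once, the median pause comes at about the 31st C/D patient. With 6 × 126/190 = 3.98 C/D patients a month, that is 31/3.98 = 7.8 months.

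The cost is a short addition to 16.33, one extra count and one table, from data already collected. There are also more false pauses. If both drugs share the same true rate, the chance of any C/D pause rises from about 2.4% to 3-4% (true 5%), from 15% to 18-22% (true 10%) and from 40% to 43-48% (true 15%).
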